2.6 ASSESSMENT TIMELINES/SCHEDULE

Each follow-up visit time point will be determined based on the date of surgery. Each follow-up visit has a specific allowed time window:

- Preoperative (within 3 months prior to surgery)
- Admission period
- 6 months post-operatively (+/- 4 weeks)

The assessment and data collection schedule is outlined in the table below.

Assessment	Preop	Operative	6 Months
Informed Consent	*		
Randomization	*		
Historical Record	*		
Operative Record		*	
OKS, AKSS	*		*
EQ-5D	*		*
Limb CT scanning			*
Independent CT Review			*
Complications		As needed	As needed

3. SELECTION AND WITHDRAWAL OF PATIENTS

3.1 INCLUSION CRITERIA

In order to be eligible to participate in this study, a patient must meet all of the following criteria.

- Knee (either unilateral or bilateral) osteoarthritis (varus deformity only)
- Male or female
- At least 20 years of age
- Patients willing to return for follow-up evaluations.

Study Specific Requirements for Principal Investigator/Site

- Principal Investigator (PI) must have experience of at least 5 TKAs of *iASSIST Knee* with *Persona* and *Persona* conventional instrument system before any study specific activities.
- Site has sufficient resources to take limb CT scanning at 6 months follow-up visit.

3.2 EXCLUSION CRITERIA

A potential patient who meets any of the following criteria will be excluded from participation in this study.

Absolute contraindications include:

- Knee degenerative diseases other than knee osteoarthritis (such as necrosis/rheumatoid arthritis)
- Too severe OA deformation (FTA: > 190 degrees/< 175 degrees)
- Active infection (or within 6 weeks after infection)
- Sepsis
- Osteomyelitis
- Any type of implant is inserted in the affected side of lower extremity
- Hip and/or foot disease on the affected side

Additional contraindications include:

- Uncooperative patient or patient with neurologic disorders who are incapable of following directions
- Diagnosed osteoporosis or osteomalacia
- Metabolic disorders which may impair bone formation
- Distant foci of infections which may spread to the implant site
- Rapid joint destruction, marked bone loss or bone resorption apparent on roentgenogram
- Vascular insufficiency, muscular atrophy or neuromuscular disease.

3.3 PATIENT WITHDRAWAL

It is recognized that the patient's participation in this study is entirely voluntary, and that he/she may refuse to participate and may withdraw from participation at any time without jeopardy to any future medical care. It is also recognized that the PI, at his/her discretion, may withdraw a subject from this study based upon his/her professional judgment. In event of subject withdrawal, applicable local procedures should be followed.

If a patient is withdrawn or rescinds their consent, a "Lost to Follow-up" CRF should be completed detailing the reason for the patient withdrawal. The PI should also notify the Ethics Committee (EC) if applicable. If a patient is withdrawn from the study, he/she should be notified of his/her removal by the PI or according to the condition set by the EC.

It is required that patients return within the defined follow-up period to complete all study assessment forms and CT scanning. Patients that miss or will not return for follow-up are not considered “protocol deviations” or “lost to follow-up.”

Specific criteria for withdrawal (if applicable)

If patients meet any of the following criteria, a “Subject Withdrawal” CRF should be completed, and below data documented on the form:

1. Patient rescinds consent in writing: Date of occurrence
2. Patient death: Reason and date of death should be documented.
3. Implant removal: Date of revision, all component part numbers removed, and reason for revision
4. Revision of metal components (Femur or Tibia)*: Date of revision, all component part numbers removed, and reason for revision

**Bearing revisions in which only the polyethylene is replaced will not be withdrawn from the study.*

Replacement of individual patients after withdrawal

Patients will not be replaced, unless they do not have surgery or intraoperatively it has been recognized the patient is not eligible for a treatment with *Persona*.

Follow-up of patients withdrawn from treatment

Patient withdrawn from the study will obtain standard medical treatment as foreseen at the investigational site.

4. PROTOCOL DEVIATION MANAGEMENT AND REPORTING

Any deviation from the protocol should be documented on the “Protocol Deviation” CRF.

5. ADVERSE EVENT MANAGEMENT AND REPORTING

Any adverse event should be documented on the “Adverse Event” CRF. A record of all adverse events, including details of the nature, onset, duration, severity, relationship to the device, relationship to the operative procedure and outcome, will be made on the relevant section(s) of the patient’s CRF. The patient will be questioned about any adverse event(s) at each subsequent follow-up assessment visit.

Any serious adverse events (SAE/SADE/USADE) must be reported to head of site and must be notified to other sites participating in this study in accordance with EC and Ethical Guidance for clinical study including human subject.

Adverse Event (AE):

An adverse event is any untoward medical occurrence in a patient receiving an investigational medical device that does not necessarily have to have a causal relationship with the device under investigation. An AE can therefore be any unfavorable and unintended sign (including abnormal laboratory finding), symptom, or condition temporally associated with the use of a medical device whether or not considered related to the medical device.

Serious Adverse Event (SAE):

A serious adverse event is an adverse event that

- a) led to death,
 - b) led to a serious deterioration in the health of the patient that
 - c) led to fetal distress, fetal death or a congenital abnormality or birth defect.
- 1) resulted in a life-threatening illness or injury,
 - 2) resulted in a permanent impairment of a body structure or a body function,
 - 3) resulted in medical or surgical intervention to prevent permanent impairment to body structure or body function, or
 - 4) required in-patient hospitalization or prolongation of existing hospitalization.

A planned hospitalization for a pre-existing condition, or a procedure required by this protocol, without serious deterioration in health, is not considered a SAE.

Adverse Device Effect (ADE):

An ADE is any untoward and unintended response to an investigational medical device.

Serious Adverse Device Effect (SADE):

A SADE is any untoward and unintended response investigational medical device that has resulted in any of the consequences characteristic of a SAE or that might have led to any of these consequences if suitable action had not been taken or intervention had not been made or if circumstances had been less opportune.

Unanticipated serious adverse device effect (USADE)

SADE which by its nature, incidence, severity or outcome has not been identified in the current version of the risk analysis report (see section 10).

6. IMPLANT RETRIEVAL AND ANALYSIS OF REMOVED IMPLANTS

Should any implant failures occur, contact the Study Manager or any other Zimmer Biomet personnel to coordinate the implant retrieval process.

7. STATISTICAL ANALYSIS PLAN

The primary analysis for the study will compare the proportion of alignment accuracy of the knee femoral or tibial components ranging +/- 3 degrees from neutral based on the 6 month postoperative CT scan for *iASSIST Knee* vs. Control (conventional instrumentation).

The primary analysis will test the null hypothesis that the proportion of tibial or femoral component alignment within +/- 3 degrees of neutral for the Investigational group (*iASSIST Knee*) is equal to that of the patients operated without *iASSIST Knee*. The alternative hypothesis is that the proportion of tibial or femoral component alignment within +/- 3 degrees of neutral for the *iASSIST Knee* group is not equal to that of the patients operated without *iASSIST Knee*.

Null Hypothesis: $H_0: \pi_A - \pi_B = 0$

Alternative Hypothesis: $H_A: \pi_A - \pi_B \neq 0$

where π_A represents the proportion of tibial or femoral alignment within +/- 2 degrees from neutral in investigational group on the 6 month postoperative CT scanning and π_B represents the proportion of tibial or femoral alignment within +/- 2 degrees from neutral in control group on the 6 month postoperative CT scanning.

If we reject the null hypothesis, we can conclude that *iASSIST Knee* are more accurate than conventional instrumentation in TKA surgery for either the tibial or femoral component alignment.

Alignment accuracy is defined as the deviation of an angle obtained from the CT scans versus a predefined angle that is accepted for an aligned knee component (refer to the Table 1). Intraoperative validation angles will also be used as targets in the *iASSIST Knee* group. A deviation of +/- 3° is considered to be within the accepted range of an aligned knee component, as reported in the literature^{7, 8}. Massé *et al.* have demonstrated 4.8% *iASSIST* and 30.4% conventional outliers of $\pm 2^\circ$ from neutral for the femur varus-valgus angle, 9.5% *iASSIST* and 60.9% conventional outliers of $\pm 2^\circ$ from neutral for the femur flexion-extension, 4.8% *iASSIST* and 30.4% conventional outliers of $\pm 2^\circ$ from neutral for the tibial varus-valgus angle and 28.6%

iASSIST and 73.9% conventional outliers of $\pm 2^\circ$ from neutral for the tibia slope⁹. The improvement of the accuracy achieved by the use of the iASSIST Knee validation feature will be evaluated as part of the study for both femur and tibia cuts in both planes. The first tibial proximal and the first femoral distal cuts will be performed and validated. If the validation values are outside of ± 2 degrees from target, the surgeon will adjust the cut as per the iASSIST surgical technique recommendations, re-cut and re-validate.

Table 1. Predefined Target Component Angles

Plane	Component	Persona component Angles
Frontal	Femoral	90
	Tibial	90
Sagittal	Femoral	defined by preoperatively
	Tibial	defined by preoperatively

SAMPLE SIZE

This sample size calculation was conducted anticipating the use of a Fisher’s exact test.

Alpha level: 5% (two-sided)

Power: 80%

Assuming we anticipate that 95% of the investigational group has an angle deviation within $\pm 2^\circ$ and that for the control group, 70% have an angle deviation within $\pm 2^\circ$, the calculation for sample size when comparing proportions is 31 patients. 50 patients per group comfortably exceeds 20% attrition. Therefore, this provides for a total of 100 patients for both arms.

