2.3 PRIMARY AND SECONDARY ENDPOINTS

Primary Endpoint

The primary study endpoint is the alignment accuracy of the knee femoral and tibial components at 6 months for the investigational group compared to the control group.

Secondary Endpoints

- Health Status assessed with the EQ-5D form ⁵
- Operating Room efficiency
 - o OR time
 - o Number of instrument trays used
- Complication rate: incidence of adverse events as well as the proportion of patients who experience at least one complication related to *iASSIST Knee* or conventional instrumentation

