7.2 HANDLING OF MISSING AND INCOMPLETE DATA

Data will be considered “missing” for the primary endpoint if this outcome cannot be determined or is unavailable for a subject. Every effort will be made to collect the data necessary to evaluate the primary endpoint. Patients who have been lost to follow-up and do not have Tibial alignment at 6 months will not be included in the primary study analysis.

Sensitivity analyses will be performed to assess the impact of missing data on the primary study analysis. These analyses may include a best-case and worst-case imputation as well as a tipping point analysis.

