7.3 DATA ANALYSES

Data will be analyzed using SAS 9.0 or higher. The Type I error rate for the primary study analysis will be 0.05. Comparisons for secondary, exploratory, and safety analyses will be two-sided comparisons using $\alpha = 0.05$, with no adjustment for multiple comparisons.

Primary Analysis: The primary analysis will be presented as both intention-to-treat (ITT) and Full Analysis set (FAS). In the ITT analysis for the primary endpoint, missing data will be treated as described in Section 7.2. A two-tailed Fisher’s Exact Chi-Square test at $\alpha = 0.05$ will be used to assess the study hypotheses and determine whether there is a statistically significant difference between investigational and control groups with regard to the proportion of patients with femoral or tibial component alignment within +/- 3 degrees from predefined angles (Table 1).

Secondary Analysis: Analyses for secondary endpoints will be FAS, and will only use those cases with complete data for the endpoint being analysed.

Continuous data (e.g. age, BMI, VAS pain) will be reported using mean, standard deviation, median, and range. Comparisons of Investigational vs Control with regard to continuous baseline and secondary outcomes will be performed using standard statistical tests and will be chosen as appropriate for the scale and distribution of the measures being analyzed. For example, a t-test, Wilcoxon test, or one-way ANOVA (as appropriate) may be performed to assess differences.

Categorical data (e.g. gender) will be reported using frequency and percentage. Comparisons of Investigational vs Control with regard to categorical baseline, secondary and safety outcomes will be performed using standard statistical tests and will be chosen as appropriate for the scale and distribution of the measures being analyzed. For example, categorical outcomes may be compared for investigational and

control groups using the Fisher's Exact test (for 2x2 tables) or the Likelihood Ratio chi-square test (for tables larger than 2x2).

Knee prosthesis survivorship will be assessed using a Kaplan-Meier analysis. Comparison of survivorship for Investigational vs Control will be done using the Log-Rank test.

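### The primary event is not defined at patient level: the plan does not say how femoral and tibial alignment, in one or two planes, combine into the single yes/no value its Fisher test needs

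*Combined protocol and SAP*

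**What the plan says.** All places are in the combined protocol and SAP.

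- **Section 2.3** sets the endpoint: "The primary study endpoint is the alignment accuracy of the knee femoral and tibial components at 6 months". It gives no plane, limit or combination rule.
- **Section 7**, opening, will "compare the proportion of alignment accuracy of the knee femoral or tibial components ranging +/- 3 degrees from neutral". The definitions of the two proportions that follow also use 'or', but with a limit of ±2 degrees.
- **Section 7**, after the hypotheses, lets a rejection support the statement that iASSIST knees "are more accurate than conventional instrumentation in TKA surgery for either the tibial or femoral component alignment".
- **Section 7** defines accuracy as the deviation of one angle from its target. **Table 1** then lists four: frontal and sagittal, femoral and tibial. Section 7 adds that intraoperative validation angles also serve as targets, in the iASSIST group only.
- **Section 7**, before Table 1, says the gain from the validation feature will be evaluated "for both femur and tibia cuts in both planes". That describes what is looked at; it is not a rule for success.
- **Section 7, Sample size**, uses one unnamed angle: "Assuming we anticipate that 95% of the investigational group has an angle deviation within" ±2 degrees, against 70% of controls.
- **Section 7.2** leaves out patients lost to follow-up who "do not have Tibial alignment at 6 months will not be included in the primary study analysis". Femoral alignment is not mentioned.
- **Section 7.3** plans one two-tailed Fisher test at 0.05 on the "proportion of patients with femoral or tibial component alignment within +/- 3 degrees" of the Table 1 angles. Its statement that multiplicity is not adjusted covers secondary, exploratory and safety comparisons, not the primary one.

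**The concern.** A Fisher test needs one yes/no value per patient, and the plan does not supply it. The readings left open include at least one component in range, both in range, separate tests per component or per angle, and one plane or both. Two analysts following the text could report different primary results from the same CT scans. The trial is non-blinded (Section 2), and nothing in the plan stops the choice being made after results are known.

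Two consequences follow. The literal 'or' scores a knee with one misaligned component as a success, which sits badly with a trial whose purpose is component accuracy. If 'either' instead means separate tests, the claim can rest on whichever component reaches significance, with no stated error control.

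**Working it through.** **Inputs.** Section 7 cites outlier rates beyond ±2 degrees (iASSIST vs conventional): femoral varus-valgus 4.8% vs 30.4%, tibial varus-valgus 4.8% vs 30.4%, femoral flexion-extension 9.5% vs 60.9%, tibial slope 28.6% vs 73.9%. The sample size paragraph gives alpha 5% two-sided, 80% power, 31 patients (read as per group), 50 per group enrolled and 20% attrition. So 50 and 40 per arm are used below.

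**The plan's own figure.** Unpooled normal formula, n = (1.960 + 0.842)² × [p₁(1−p₁) + p₂(1−p₂)] / (p₁−p₂)²:
- 95% vs 70%: 7.849 × 0.2575 / 0.0625 = 32.3, so 33. The arcsine formula gives 31.3, so 32.
- Unrounded frontal rates, 95.2% vs 69.6%: 30.8, so 31.

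The 31 is therefore reproduced, to within two patients or exactly, by a single frontal angle. Exact Fisher needs 39 per arm for 95% vs 70%; 50 and 40 per arm give 90% and 82%.

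**Combining two frontal components.** Let q be the outlier rate per component (0.048 and 0.304) and φ the correlation between components. The documents give no φ, so it is an assumption, taken as equal in both arms.
- P(both out) = q² + φq(1−q)
- At least one in range = 1 − P(both out)
- Both in range = 1 − 2q + P(both out)
- Exactly one out = 2[q − P(both out)]

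Example, controls at φ = 0.5: 0.0924 + 0.5 × 0.2116 = 0.198. At least one is in range in 80.2%, both in 59.0%, and exactly one is out in 21.2%.

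Exact two-sided Fisher power at 50/40 per arm:

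| φ | At least one in range, iASSIST vs control | Power | Both in range, iASSIST vs control | Power | Controls with exactly one out |
|---|---|---|---|---|---|
| 0 | 99.8% vs 90.8% | 29%/15% | 90.6% vs 48.4% | 99.7%/98.7% | 42% |
| 0.3 | 98.4% vs 84.4% | 60%/43% | 92.0% vs 54.8% | 99%/97% | 30% |
| 0.5 | 97.5% vs 80.2% | 72%/59% | 92.9% vs 59.0% | 98%/95% | 21% |
| 0.7 | 96.6% vs 75.9% | 82%/72% | 93.8% vs 63.3% | 96%/92% | 13% |
| 1 (single angle) | 95.2% vs 69.6% | 91%/84% | 95.2% vs 69.6% | 91%/84% | 0% |

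**Adding the second plane** (independent angles assumed). A component is in range only if both its planes are:
- iASSIST: femoral 0.952 × 0.905 = 0.862; tibial 0.952 × 0.714 = 0.680.
- Control: femoral 0.696 × 0.391 = 0.272; tibial 0.696 × 0.261 = 0.182.
- At least one component in range: 1 − 0.138 × 0.320 = 95.6%, against 1 − 0.728 × 0.818 = 40.4%. Power exceeds 99% at either size.

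**Separate component tests.** Nominal family-wise error under independence is 1 − 0.95² = 9.75%, and at most 10%. Fisher is conservative: its size at 50 per arm is 0.031, 0.026, 0.018 and 0.007 at true in-range rates of 70%, 82.5%, 90% and 95%. Two independent tests then give 6.0%, 5.2%, 3.5% and 1.4%.

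**Holm at the cited frontal rates.** Power for one angle at alpha 0.025 is 0.864 (50 per arm) and 0.724 (40). With φ = 0:
- Per component: 0.864 + (0.914 − 0.864) × 0.864 = 0.907 at 50; 0.724 + (0.841 − 0.724) × 0.724 = 0.809 at 40.
- At least one: 1 − 0.136² = 98% at 50; 1 − 0.276² = 92% at 40.

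Simulation over φ 0 to 0.5 gives about 90% (50) and 79–81% (40) per component, and 95–98% (50) and 86–92% (40) for at least one.

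**The case against.** The strongest reply is that the sizing shows what was meant. Accuracy is defined for one angle, and 95%/70% matches each cited frontal angle, so 'femoral or tibial' may be shorthand for a test per component. Section 2.3 may only list what is measured, so its 'and' is weak evidence for a both-components event. The validation sentence suggests that component results in both planes will be looked at, so a misaligned component need not disappear from the report.

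Much of this stands, and it limits what can be claimed:
- A reader might infer that the trial has 15% or 29% power. That needs literal 'or', frontal angles only and zero correlation together. At φ = 0.7 the figure at 50 per arm is 82%, and with both planes required it exceeds 99%.
- A reader might infer that the false-positive rate doubles. The nominal figure is near 10%, but with Fisher the realised rate for two tests is about 5–6% or lower.
- A reader might reduce the problem to a choice between two readings. More are open, including separate tests of four angles.

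The reply does not supply the missing rule. Section 7.3 still describes one test on one proportion of patients, which is not a test per component, and no text names the planes.

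**Conclusion.** The concern holds as an undefined primary event. It does not rest on a demonstrated loss of power or a large error inflation. The choice of rule matters: with the cited ±2 degree frontal rates and 50 per arm, power runs from 29% (at least one in range, φ = 0) to 99.7% (both in range, φ = 0), with the single angle at 91%. These figures rest on the cited rates holding in this trial and on an assumed φ common to both arms; the two-plane figure also assumes independence.

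Section 7.3 states the test at ±3 degrees, while the definitions of the two proportions and the sizing use ±2. A reader might want to carry the power figures over to ±3. The documents give no ±3 degree rates, so no power can be stated for that limit.

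**What to change.** Before CT data are analysed:

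1. **Define one primary event:** both femoral and tibial components in range of their targets, in named plane(s), tested once at two-sided 5%, with component results secondary. For the frontal plane at ±2 degrees and φ 0 to 0.5, power is 98–99.7% at 50 per arm and 95–99% at 40. **Alternatively,** keep component-specific primary tests under Holm, which fits the single-angle sizing, at the power shown above.
2. **Drop the uncontrolled claim for either component.** Conclude superiority only if the null is rejected and the iASSIST proportion is the higher one.
3. **Use the same Table 1 targets in both arms** for the primary event, and reconcile this with the Section 7 sentence that makes validation angles targets in the iASSIST group.
4. **Align the tibial-only exclusion** in Section 7.2 with the chosen event.
5. **Reconcile the ±2 and ±3 degree limits** in the same revision.

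The cost is SAP wording; the CT measurements are unchanged. The sponsor gives up the unadjusted either-component claim. Under Holm, power per component falls only slightly from the unadjusted 91%/84% at 50/40 per arm, to about 90% and 79–81%.

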2. STUDY DESIGN

The study is a prospective, non-blinded, randomized multi-center study, comparing the use of *iASSIST Knee* versus conventional instrumentation in the hands of experienced surgeons. A total of 100 subjects will be recruited prospectively and randomized according to a 1:1 scheme.

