2.5 ASSESSMENT PARAMETERS AND METHODS

Preoperative Data

After the patient has been consented he/she will be assigned randomly to either the investigational or the control group. Historical information will be collected, a detailed medical history will be obtained and a physical examination will be performed (including height and weight). Current medications and smoking history, if applicable, will also be recorded. A baseline OKS, AKSS and EQ-5D will be collected.

Clinical Assessments

OKS and AKSS will be used to assess the difference between the investigational and the control group. This assessment will be completed preoperatively and at 6 months post-operatively.

Patient Questionnaires

EQ-5D⁵ will be taken preoperatively and at 6 months post-operatively.

EQ-5D: Descriptive system of health-related quality of life states consisting of 5 dimensions (mobility, self-care, usual activities, pain/discomfort, anxiety/depression).

Radiographic Assessments

The scan will be performed preferably using the Perth CT protocol (Chauhan et al., 2004). Patient is placed in the supine position with legs rotated into the AP position. The legs should be in maximum tolerable extension. Immobilization sponges may be used as necessary. Allow table movement to cover from ASIS to distal talus. It is preferable that the patient is positioned feet first into the CT gantry. Perform an AP and a lateral scout to cover from ASIS to the mid talus. Scanning parameters will differ according to the CT scanner used and optimal parameters must be standardized based on its own working conditions. Ensure the scan is a low dose scan. Aim to have an effective dose of 2-3 mSv. Helical scan should cover from just above acetabulum to just below ankle joint. FOV should cover both legs. Image reconstruction 2 mm thickness at 1.6 mm interval is desirable. Bone and soft tissue reformats.

Each clinical site sends the scanned image to the independent reviewer with DICOM format after removal of personal information from the image.

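### The sagittal targets have no stated rule, recording point or lock before open allocation, and the iASSIST arm alone has a second target, so the sagittal reference can depend on the arm

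*Combined protocol and SAP*

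**What the plan says.** Section 7 defines accuracy as the difference between the CT angle and a predefined Table 1 angle. Section 7.3 then tests, with a two-tailed Fisher test, the proportion of patients with "femoral or tibial component alignment within +/- 3 degrees from predefined angles (Table 1". Table 1 sets both frontal targets at 90. Its femoral and tibial sagittal rows both read "defined by preoperatively", with no value, rule, source image, responsible role or date. Section 7 puts the sagittal plane in scope by promising an evaluation "for both femur and tibia cuts in both planes".

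Section 7 also states: "Intraoperative validation angles will also be used as targets in the" iASSIST Knee group. There is no counterpart for the control group.

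Section 2 calls the trial a "prospective, non-blinded, randomized multi-center study". On timing, Section 2.5 says: "After the patient has been consented he/she will be assigned randomly to either the investigational or the control group". Section 2.6 allows the preoperative visit up to 3 months before surgery.

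**The concern.** A deviation is only as sound as the reference it is measured from. For two of the four Table 1 angles the plan does not say what the reference is, where it is written down, or by when it must be final. In an open trial that randomises straight after consent, the plan therefore permits a sagittal target that is chosen, revised or reconstructed by someone who knows the arm. One arm also has an extra candidate target that the other cannot have. If the reference differs systematically between arms, a difference in the proportion in range can appear without any difference in surgical accuracy, or a real difference can be hidden. Reading the CT independently does not protect against this, because the reader controls the measured angle and not the target.

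**Working it through.** The plan gives no figure for this point, so there is none to reproduce, and the point does not depend on the sample size calculation. The check sets the sections side by side; a calculation then shows how the mechanism works.

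**1. What the endpoint needs.** Deviation = 6-month CT angle − target, and a component is in range if |deviation| ≤ 3 degrees (Section 7.3). Table 1 supplies a number for two of the four targets (frontal femoral and tibial, 90 each) and none for the two sagittal ones.

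**2. Where a sagittal target could be recorded.**
- Section 2.4 A, preoperative: consent, randomization, enrollment form, historical record, OKS, AKSS, EQ-5D. No planned angle.
- Section 2.4 B, Operative Form: OR time, trays, patella resurfacing, component information, approach. No planned or validation angle.
- Section 2.5: history, examination, medications, smoking, scores. No planned angle. The independent reviewer is sent the CT image; a target is not mentioned.
- Section 2.6 table: no planned angle. The only imaging listed is the 6-month CT.

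**3. Order of events.** Randomization is listed directly after consent (Sections 2.4 A and 2.5), and the study is not blinded (Section 2). No section requires the sagittal target to be final before the envelope is opened. The sealed opaque envelopes of Section 7.1 protect the allocation sequence; they do not protect a target set after opening.

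**4. Two targets in one arm.** Section 7 names the Table 1 angle for everyone and adds the intraoperative validation angle for iASSIST only, without saying which governs the primary analysis. Section 7 goes on to describe validation as a check made on the cut. If the validation angle is a reading of the cut itself, scoring against it would partly measure agreement between the device and the CT, and that target would move with the achieved result.

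**5. Illustration of the mechanism.** These assumptions are not in the documents: both arms have identical, normal sagittal errors centred on the true target, with 70% in range. Patients retained per arm: 50 × (1 − 0.20) = 40, using the 20% attrition in Section 7. The test is a two-sided Fisher test at 0.05, with power by full enumeration.

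*(a) The target in one arm follows the achieved angle.* Let it absorb a fraction r of each deviation. With limit L and SD = L / z(0.85), the apparent proportion in that arm is 2Φ(L / [SD(1 − r)]) − 1. L cancels, so limits of 2 and 3 degrees give the same result.

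| r | Apparent rate, affected arm | Other arm | Fisher rejection |
|---|---|---|---|
| 0 | 70% | 70% | 2.8% |
| 0.10 | 75% | 70% | 4.9% |
| 0.25 | 83% | 70% | 21.6% |
| 0.50 | 96% | 70% | 87.7% |

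*(b) The target in one arm is displaced by a constant δ.* With L = 3, SD = 3 / z(0.85) = 2.89 degrees, and the apparent proportion is Φ((3 − δ)/2.89) − Φ((−3 − δ)/2.89).

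| δ (degrees) | Apparent rate, affected arm | Other arm | Fisher rejection |
|---|---|---|---|
| 1 | 67% | 70% | 3.4% |
| 2 | 59% | 70% | 11.6% |
| 3 | 48% | 70% | 43.7% |

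Mechanism (a) flatters the affected arm and (b) penalises it. Small arm differences in the target do little; larger ones can create a false difference. Nothing in the documents says which values of r or δ are realistic.

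**The case against.** The strongest reply is that the plan is silent on these matters, which is not the same as being wrong.

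- **Who, when and at what level.** A reader might infer that the surgeon sets a patient-specific target already knowing the arm. The documents do not say so. The Table 1 wording is incomplete and could mean a value per patient, per site or per study, and nothing dates it relative to randomization. With one value for the whole study, arm dependence of the preoperative target would largely disappear. This stands: the supportable claim is that the target can depend on the arm, not that it does.
- **Whether it is recorded.** A reader might infer that the database will lack the reference. The CRFs are not in the documents, and the enrollment form and historical record are not itemised. The lists in Sections 2.4 and 2.6 are not field-level: height, weight and smoking history are required by Section 2.5 and named in neither. This also stands, so the claim is limited to content that the protocol describes.
- **Weight in the primary endpoint.** The hypotheses in Section 7 are framed around neutral, while Section 7.3 cites Table 1. The planning rates of 95% and 70% sit close to the cited pilot's frontal results (100 − 4.8 = 95.2% and 100 − 30.4 = 69.6% in range), not its sagittal ones. How much the sagittal plane counts is therefore unclear. But Section 7.3, which describes the test, does not exclude it.
- **Size.** A reader might use the pilot's large sagittal differences (60.9 − 9.5 = 51.4 points for femoral flexion, 73.9 − 28.6 = 45.3 for tibial slope) to size the bias. Those outliers were counted from neutral, not from a preoperative target, so they do not measure it. Nor would a target error shared by both arms show it, since such an error does not make the reference depend on the arm.

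None of this answers the iASSIST-only target, which is written in the plan.

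**Conclusion.** The point holds as a gap in specification that leaves open a route to bias. Both sagittal targets lack a rule, a described place of record and a lock before open allocation, and the iASSIST arm alone has a second target with no order of precedence. The sagittal reference can therefore depend on the arm. The size of any effect is unknown; the rejection rates above rest on assumed normal errors and assumed target shifts, and they show only that the effect can go either way and need not be small. The frontal targets are fixed at 90 and are unaffected. The documents do not support saying that the primary result will be biased or that the sagittal angles cannot be scored. This is a cheap improvement, worth making before the first envelope is opened.

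**What to change.** 1. Record the planned femoral and tibial sagittal angles on a dated preoperative form, in both arms, before the randomisation envelope is opened. Add the item to Section 2.4 A and to the Section 2.6 table.
2. State in Section 7 and Table 1 that the sagittal deviation in the primary analysis is the 6-month CT angle minus this locked value, in both arms.
3. Amend the Section 7 sentence on intraoperative validation angles so that they serve only a separate, descriptive analysis within the iASSIST arm. Otherwise it would contradict item 2.

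This prescribes no target angle. It costs two form fields and a few sentences. The downside is that the target must be recorded before allocation is known, and a later change of plan then counts as deviation.
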